## **5. AMENDMENTS AND UPDATES**

V 1.0 dated 11 December 2020

V 2.0 dated 8 February 2021

- Changes as recommended by the ethics committee Medizinische Fakultät Heidelberg in chapter 9.2.3 Study visits
- Changes as recommended by the ethics committee Medizinische Fakultät Heidelberg in chapter 10 Protection of human subjects
- Two additional further outcomes added in chapter 9.3.2.3 Further Outcomes as recommended by TSTAT.

## 6. MILESTONES

Milestone	Planned Date
IRB/IEC approval	Feb 2021
Start of data collection	Feb 2021
End of data collection	Feb 2023
Final report of study results:	Oct 2023

## 7. RATIONALE AND BACKGROUND

The term interstitial lung disease (ILD) encompasses a large group of > 200 parenchymal pulmonary disorders, of which the majority are classified as rare. The most widely studied and most common ILD is Idiopathic Pulmonary Fibrosis (IPF). It is characterized by progressive fibrosis, lung scarring and a radiological pattern known as usual interstitial pneumonia (UIP). Several other ILDs (such as hypersensitivity pneumonitis (HP), rheumatoid arthritis-associated ILD (RA-ILD) and Systemic Sclerosis-ILD (SSc-ILD)) may present a progressive fibrosing phenotype as well.

Given their overlapping clinical, radiological and pathological presentations, a terminology to describe these patients may be “chronic fibrosing ILD with a progressive phenotype”.

[figure not shown]

Figure 7:1 Classification of Interstitial Lung Disease (from ).

Progressive fibrosis of the lung parenchyma is self-sustaining and causes progressive deterioration in lung function, respiratory symptoms such as dyspnea. It therefore increases the risk of early death. Cough and quality of life are also part of the progressive deterioration.

Scientific evidence shows from both the TOMORROW and the INPULSIS-1 and -2 trials that nintedanib is effective and its side effects are manageable for the treatment of IPF in patients with different degrees of lung function impairment. The available real-world data confirmed the safety and efficacy profiles of nintedanib in IPF that were established in clinical trials.

Furthermore, nintedanib was shown to significantly slow the annual rate of decline in the forced vital capacity (FVC) in patients with progressive fibrosing ILD. In the INBUILD trial, which included ILD patients with a variety of underlying interstitial lung diseases, the magnitude of this benefit was similar to that previously described in the IPF population. The treatment effect was consistent for patients with a UIP-like pattern as well as other patterns on HRCT, and also consistent across pre-defined subgroups of ILD diagnoses.

Insights from INBUILD further support the initial hypothesis that common traits in fibrotic mechanisms explain the clinical similarity of IPF and other fibrosing ILDs. In SENSCIS, patients suffering from SSc-ILD and treated with nintedanib were shown to have a reduced annual rate of decline in FVC vs patients in the placebo arm; though no clinical benefit of nintedanib was observed for other manifestations of systemic sclerosis.

To our knowledge, the effects of an antifibrotic therapy with nintedanib on the patient-reported outcomes (PRO) dyspnea or cough has only been investigated scarcely, especially in a real-world cohort.

This may partly be due to a lack of well-established, patient questionnaire that focuses on such symptoms. The living with pulmonary fibrosis questionnaire (L-PF) was used in the INBUILD trial. The complete L-PF questionnaire is a 44 item questionnaire with two modules: 1) symptoms (23 items) and 2) impacts (21 items). In this NIS, we will use the whole L-PF questionnaire. Its symptom part consists of three subdomains a) dyspnea b) cough c) fatigue (together 23 items). Each question is answered by the patient indicating one tick-box answer per question. Only one statement can be chosen. L-PF symptoms domain scores range from 0 to 100; the higher the score, the greater the impairment. An improved understanding of the patients' situation will benefit from further investigation of this instrument in a real-world setting.

Results from INBUILD show that differences in the change of the score for cough and dyspnea from baseline to 52 weeks were statistically significant in favor of nintedanib, comparing treatment arm with placebo. Those differences were small. The meaningful threshold ("MCID") has not been established for the L-PF questionnaire so far.

By applying the L-PF questionnaire and capturing the FVC, we want to further investigate whether there are correlations between change of FVC ( $\Delta$ FVC: 52 weeks vs baseline) and change in cough or dyspnea score ( $\Delta$ cough,  $\Delta$ dyspnea: 52 weeks vs baseline) respectively, in this real-world patient population as well. Data from a real-world patient population may strengthen the data basis on this issue.

We are planning to include patients with chronic fibrosing ILD with a progressive phenotype excluding IPF patients. Regarding their specific form of chronic fibrosing ILD with a progressive phenotype, patients will be enrolled based on their phenotype and not on predetermined ILDs. – The study will include a pre-specified analysis of outcomes according to specific diagnoses, as the L-PF questionnaire was specifically developed for and validated in patients with chronic fibrosing ILD with a progressive phenotype, except IPF. Furthermore, we plan to investigate a possible change in dyspnea and cough scores under nintedanib treatment, to answer the question whether nintedanib has a direct effect on PROs in a real-world patient population.

All patients will receive nintedanib according to standard of care; i. e. there will be no untreated comparison group in this study. Given the natural course of the disease, this poses a limitation in that results from the treated group will be difficult to interpret meaningfully in the absence of a reference group to demonstrate how the study outcomes appear in the absence of treatment in the real world setting. However, data from this study will complement the data from INBUILD and INBUILD-ON, which can in turn provide context to this study.

In conclusion, this prospective, non-interventional study (NIS) aims to assess a possible correlation between the reduction of FVC decline and symptomatic burden under nintedanib treatment for 52 weeks in 100 patients with chronic fibrosing ILD with a progressive phenotype, measured as a possible change in dyspnea and cough scores from baseline using the L-PF questionnaire in a real-world patient population.

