## 9.5 STUDY SIZE

In the INBUILD trial, patient groups on placebo vs nintedanib therapy differed in both their loss of FVC and dyspnea and cough symptom scores in the L-PF questionnaire (Figure 9.5:1; see below).

[figure not shown]

Figure 9.5:1 Changes from baseline to week 52 in L-PF symptoms dyspnea (left) and cough (right), domain scores respectively, seen in INBUILD

$\Delta$ FVC,  $\Delta$ dyspnea and  $\Delta$ cough symptom scores from INBUILD (see Table 9.5:1 below) were applied to estimate sample sizes.

Correlations between the change from baseline to week 52 in FVC (both FVC in mL and FVC as % predicted) and the change from baseline to week 52 in both L-PF dyspnea symptom score and cough symptom score measured by Pearson's correlation coefficient were  $\rho \approx -0.3$  in the Nintedanib arm of the treated set (see Table 9.5:1 below).

Table 9.5:1

Pearson correlation between the change from baseline to week 52 in FVC and the change from baseline to week 52 in L-PF symptoms scores in the Nintedanib arm (results were similar for the total population.)

Pearson correlation (change from baseline at week 52) between FVC and L-PF symptoms	Coefficient	95% Confidence interval	
		Lower	Upper
L-PF symptoms dyspnoe score and ...			
FVC in ml	-0.35	-0.45	-0.23
FVC (% predicted)	-0.37	-0.47	-0.26
L-PF symptoms cough score and ...			
FVC in ml	-0.26	-0.37	-0.14
FVC (% predicted)	-0.26	-0.37	-0.14

Currently, a meaningful threshold (“MCID”) has been published for neither the cough nor the dyspnea domain of the L-PF. However, should that information become available during the study, study results will be discussed in relation to meaningful thresholds (“MCID”) values.

Given a correlation  $\rho$  between change from baseline to week 52 in FVC [% pred.] and change from baseline to week 52 in dyspnea symptom score as well as change from baseline to week 52 in FVC [% pred.] and change from baseline to week 52 in cough symptom score of approximately -0.3, then 84 patient data sets would be required for evaluation. Assuming an estimated drop-out rate of approx. 15 % 100 patients will have to be recruited for this study. With this patient number (N = 84) and the assumption of a Pearson correlation of -0.3, the overall type I error is protected at the two-sided 0.05 level with a power of 80 %.

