## 7. VARIABLES

The following parameters will be collected and assessed at visits 1 to 5, as applicable:

- Patient demographics (age, gender, height, weight)
- Smoking history, current status (current smokers, former smokers, and never smokers) and pack-years
- History of ILD, including ILD entity and HRCT pattern (where available in patient documentation)
- current DLCO measures (where available in patient documentation)
- Concomitant diseases
- Previous ILD therapies in the 6 weeks before visit 1
- Current ILD related or other relevant concomitant medication
- FVC (mL and % pred.; if available in patient data)
- Severity of disease as per the treating physician's estimation (if available in patient data)
- L-PF questionnaire, completed by patient
- Safety: ADRs (serious and non-serious), fatal AEs, pregnancies during the study
- Rationale for treatment discontinuation (if applicable)
- Intention to continue or discontinue treatment with nintedanib (Ofev®) after the study (yes/no)
- Further treatment options yes/no, as applicable

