**7.3 Covariates**

Covariates for adjustment will include the following disease characteristics:

- Pulmonary function test (DLCO) result [% pred] at baseline
- FVC result [% pred.] at baseline
- FVC result [mL] at baseline

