## 10. DATA ANALYSIS

**Treated Set (TS):** All patients with signed informed consent who received at least one dose of nintedanib will be included in the treated set.

**Per Protocol Set (PPS):** All patients from the treated set who met all inclusion and exclusion criteria and did not violate any important protocol deviations.

Important protocol deviations:

- Dose interruption of nintedanib for more than 12 weeks and/or initiation of another antifibrotic therapy during the observation phase of the study.
- Missing patient questionnaires or other variables necessary for assessment of the primary study outcome
- Last patient visit completely missing (if no data is available for week 52)
- No FVC measurement available within 3 months prior to inclusion and FVC was not evaluated at baseline

All analyses will be performed on the treated set. Primary and secondary outcomes will be analysed for patients who have available data for the analysis of the efficacy endpoints. Additionally, all analyses for baseline and efficacy will be done on the per protocol set if  $\geq 10\%$  of the treated set is omitted.

All analyses on the treated and per protocol set will be performed using the method of time windowing: Only data will be used that was documented at performed visits within  $\pm 6$  weeks of the planned visit date (see 6.4 STUDY VISITS). For purpose of sensitivity primary and secondary endpoints will also be analysed without time windowing.

No subgroup analyses are planned due to the small number of patients.

For categorical variables summary tabulations of the number and percentage (%) relative to the treated set (unless otherwise specified, all patients in the patient set whether they have non-missing values or not) within each category of the parameter will be presented. The category missing will be displayed only if there are actually missing values.

For continuous variables number of values, mean, standard deviation, minimum, 25th percentile, median 75th percentile, maximum and number of missing values will be presented.

Percentages will be rounded to two decimal places.

No interim analysis is planned.

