## 10.1 Main analysis

Due to the observational nature of the study, all analyses are exploratory. No weighting will be applied to either of the co-primary endpoints.

For the analysis of the primary outcomes

- Correlation between change from baseline to week 52 in FVC [% pred.] and change from baseline to week 52 in dyspnea symptom score
- Correlation between change from baseline to week 52 in FVC [% pred.] and change from baseline to week 52 in cough symptom score

Pearson measures of correlation along with 95% two-sided confidence intervals and the two-sided p-values will be provided.

For the secondary outcomes

[figure not shown]
- Correlation between change from baseline to week 52 in FVC [mL] and change from baseline to week 52 in dyspnea symptom score
- Correlation between change from baseline to week 52 in FVC [mL] and change from baseline to week 52 in cough symptom score

Pearson measures of correlation along with 95% two-sided confidence intervals and the two-sided p-values will be provided.

The secondary outcomes

- absolute change from baseline in L-PF symptoms dyspnoea domain score between week 52 and baseline
- absolute change from baseline in L-PF symptoms cough domain score between week 52 and baseline

will be analyzed using a restricted maximum likelihood (REML) based repeated measures approach. Analyses will include the fixed, categorical effect of visit, as well as the continuous, fixed covariates of baseline and baseline-by-visit interaction. An unstructured (co)variance structure will be used to model the within-patient measurements.

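### The protocol commits to an analysis by diagnosis that the SAP rules out, so the plan does not show whether the pooled FVC–symptom correlation also holds within diagnoses

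*Protocol*

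**What the plan says.** **Protocol.** The abstract (Rationale and background) and section 7 carry the same sentence: "The study will include a pre-specified analysis of outcomes according to specific diagnoses". The reason attached to it is that the L-PF was developed for and validated in this non-IPF population. The preceding sentence says that "patients will be enrolled based on their phenotype and not on predetermined ILDs", so the cohort mixes ILD entities by design. The commitment is not repeated in section 8 or in the visible outcome and analysis sections (9.3.2.1, 9.3.2.2, 9.7.1).

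**SAP.** Section 10 says: "No subgroup analyses are planned due to the small number of patients". For the primary outcomes, section 10.1 says: "Pearson measures of correlation along with 95% two-sided confidence intervals and the two-sided p-values will be provided". No stratification or adjustment is attached to them. Section 7.3 begins "Covariates for adjustment will include the following disease characteristics" and then lists only baseline DLCO and baseline FVC (in % predicted and in mL). Diagnosis is not listed, and section 10.1 brings none of these covariates into the correlations. ILD entity is among the collected variables in section 7, where the patient documentation has it. The extra analyses in section 10 are a per protocol set analysis (if at least 10% of the treated set is omitted) and a repeat of the primary and secondary endpoints without time windowing. Neither involves diagnosis.

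**The concern.** Both statements are current text and they cannot both be followed. Small numbers were not new information when the SAP was written, because the protocol that made the commitment already planned 100 patients.

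This matters for interpretation. Each patient contributes one pair of changes, so the pooled r describes how the changes vary together across all patients. Part of that may come from patients who share a diagnosis, and part from diagnoses that differ on average in both FVC loss and symptom change. Protocol section 10.3 hopes that symptom change may serve as an early sign of progression noticed by the patient. For that use it helps to know whether the association is also present among patients with the same disease. The visible plan gives no means of seeing this.

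**Working it through.** **1. The plan's own figure.** Inputs from Protocol section 9.5: "the assumption of a Pearson correlation of -0.3", two-sided 0.05, 80% power, 84 evaluable, about 15% drop-out, 100 recruited.

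- n = ((1.960 + 0.842)/atanh(0.3))² + 3 = 84.93, rounded up to 85.
- Power at n = 84 is 79.6% by plain Fisher z, or 80.0% with the bias-corrected form.
- 84/0.85 gives 99 and 85/0.85 gives 100.

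The stated 84 and 100 reproduce, so the sample size is not in dispute.

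**2. What mean differences between diagnoses could contribute.** The documents give neither the diagnosis mix nor the spread between diagnoses, so these inputs are assumptions. Take two equal groups with within-group SD 1 on both changes and zero correlation inside each group. Let the means differ by d on FVC change and by d in the opposite direction on score change. Then:

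pooled r = -(d²/4) / (1 + d²/4)

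- d = 0.5: -0.0625/1.0625 = -0.06
- d = 1: -0.25/1.25 = -0.20
- d = 1.31: about -0.30

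With five equally spaced groups, reaching -0.30 needs the extreme groups to be about 1.85 within-group SDs apart on both variables.

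**3. The same illustration as test results.** Simulation with 20,000 runs, n = 84, two, three or five equal groups, zero correlation within groups, and means aligned in opposite directions:

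| Share of variance of both changes due to diagnosis | Pooled r (about) | Pooled test significant | Entity-adjusted test significant |
|---|---|---|---|
| 10% | -0.10 | about 15% | about 5% |
| 20% | -0.20 | 45–46% | about 5% |
| 30% | -0.30 | 81–83% | about 5% |

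**4. Is small size a reason to omit everything?** For separate correlations the intervals are wide. At r = -0.30, Fisher z with SE 1/√(n - 3) gives these 95% CIs:

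| n in the diagnosis group | 95% CI |
|---|---|
| 40 | -0.56 to 0.01 |
| 28 (84/3) | -0.61 to 0.08 |
| 20 | -0.66 to 0.16 |
| 17 (about 84/5) | -0.68 to 0.21 |

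Power would be 34% at n = 28 and 21% at n = 17. This supports having no tests by diagnosis.

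A single correlation adjusted for k diagnosis groups uses n - 3 - (k - 1) in place of n - 3. At n = 84 and r = -0.3:

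| k | Power | n for 80% power |
|---|---|---|
| 1 (unadjusted) | 79.6% | 85 |
| 2 | 79.1% | 86 |
| 3 | 78.6% | 87 |
| 5 | 77.5% | 89 |
| 6 | 77.0% | 90 |

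The loss is 0.5 to 2.6 percentage points, and only in the supportive analysis.

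**The case against.** **The pooled r is the stated target.** Protocol section 8 asks for the correlation in patients with the progressive phenotype, and section 7 argues for common fibrotic mechanisms. The planning correlations come from the INBUILD nintedanib arm, which also mixed ILDs, and no adjustment for diagnosis is mentioned. If one disease loses more FVC and worsens more in symptoms, that belongs to the population association. This stands. A reader might infer that the pooled r is an artefact, or that adjusting for diagnosis would isolate change within the individual patient. The documents support neither. An entity-adjusted r is still a correlation between patients, within diagnosis, and it answers a second question.

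**The differences are hypothetical.** This also stands. Nothing in the documents shows that diagnoses differ by the amounts assumed above. The INBUILD statement about consistency across diagnoses concerns the treatment effect and does not settle the matter either way.

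**The commitment is rationale text and the omission is open.** The protocol does not say that the by-diagnosis analysis was meant to detect confounding; the reason it gives concerns the questionnaire. SAP section 4 and the history table record changes between SAP versions, so their silence does not show that an analysis was removed quietly. Both points are fair, but the two documents still conflict.

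**Other text may fill the gap.** Protocol 9.3.2.3 (Further Outcomes, named in section 5) is not visible, the numbering skips from 9.7.1 to 9.7.3 and from SAP 10.1 to 10.3, and the table shells are a separate document. A by-diagnosis display or an adjusted model could be there. The SAP sentence on subgroups would then conflict with a by-diagnosis display and would still need correcting.

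**Conclusion.** The concern holds as an unreconciled conflict between protocol and SAP, with a consequence for interpretation. On the visible text, the plan cannot show whether the pooled correlation is also present among patients with the same diagnosis. The size of any contribution from differences between diagnoses is unknown. The values of -0.06 and -0.20 rest on two equal groups, zero within-group correlation and opposite-signed mean differences of 0.5 and 1 SD. A pooled r of -0.3 arising wholly in this way would need large, aligned differences.

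A reader might take the simulated 45–46% as a false-positive rate of the planned test. It is not: in that scenario the pooled correlation is truly non-zero, so the test is right about its own target. All analyses are labelled exploratory, and no confirmatory error rate is affected. The SAP's reason of small numbers is sound against separate tests by diagnosis. It does not justify leaving out a descriptive display or one adjusted correlation.

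**What to change.** Keep the pooled Pearson r as primary and replace the subgroup sentence in SAP section 10 with:

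> Changes in FVC and L-PF scores, and Pearson r with 95% CI where group size allows, are shown descriptively by ILD entity without tests, with rare or unknown entities pooled as other/unknown. As a supportive analysis, the primary correlations are also given adjusted for ILD entity (partial correlation).

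Any minimum group size for showing r should be stated as an SAP choice; the protocol text available does not pre-specify one. The other/unknown category is needed because entity is recorded only where the patient documentation has it. If the sponsor prefers not to add these analyses, the SAP should at least record the omission as a justified departure from the protocol.

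The cost is SAP wording and one or two tables, with no new data item. The downsides are wide by-entity intervals that must be labelled descriptive, and the small loss of precision in the adjusted correlation shown above.

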## **8. RESEARCH QUESTION AND OBJECTIVES**

### **Primary objective**

The primary objective of this observational study is to investigate the correlation between changes from baseline at 52 weeks in FVC [% pred.] and changes from baseline at 52 weeks in dyspnea score [points] or cough score [points] as measured with the L-PF questionnaire over 52 weeks of nintedanib treatment in patients suffering from chronic fibrosing ILD with a progressive phenotype (excluding IPF):

- Correlation between change from baseline to week 52 in FVC [% pred.] and change from baseline to week 52 in dyspnea symptom score
- Correlation between change from baseline to week 52 in FVC [% pred.] and change from baseline to week 52 in cough symptom score

### **Secondary objectives**

- Correlation between change from baseline to week 52 in FVC [mL] and change from baseline to week 52 in dyspnea symptom score
- Correlation between change from baseline to week 52 in FVC [mL] and change from baseline to week 52 in cough symptom score
- Absolute change from baseline in L-PF cough symptom score at week 52
- Absolute change from baseline in L-PF dyspnea symptom score at week 52

Primary and secondary objectives will be analyzed for the treated set.

